1.3.1 Nivolumab In Hepatocellular Carcinoma

Nivolumab was initially tested in hepatocellular carcinoma in the phase I/II Checkmate-040 study [3]. This was an open-label, non-comparative dose escalation and expansion trial. A total of 262 subjects were treated in the two phases of the study. In the dose-escalation portion, the overall response rate was 15%, with a disease control rate of 58% and a median overall survival of 15.0 months. In the dose expansion phase, an objective response rate of 20% was demonstrated, and median survival was not reached in the overall population. Response rates were similar regardless of viral hepatitis status or prior treatment with sorafenib. Toxicity was manageable, with 25% grade 3/4 adverse events, most commonly rash (23%), AST increase (21%), ALT increase (15%), lipase increase (21%), amylase increase (19%), and pruritis (19%). Treatment-related serious adverse events were seen in 6% of patients in the dose-escalation of cohort. Only 20% of subjects had PD-L1 expression of > 1% by IHC, and this did not correlate with response rate. Based on the results of this study, nivolumab received accelerated approval from the FDA for HCC. A phase III trial (Checkmate-459) comparing sorafenib to nivolumab for the initial treatment of advanced HCC is ongoing.

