2.2 Secondary Objectives

- To determine PFS and DOR of abemaciclib plus nivolumab in HCC as measured by both RECIST v 1.1 and iRECIST. To measure ORR by iRECIST. To summarize OS using Kaplan-Meier methods
- To determine toxicity rates by category using CTCAE v. 5.0

[figure not shown]

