^a Reflex/confirmation dependent on regulatory requirements and/or testing availability.

Table 4: Dose Modification and Management — Hematologic Toxicities

Monitor complete blood counts prior to the start of abemaciclib therapy, every 2 weeks for the first 2 months, monthly for the next 2 months, and as clinically indicated.	
CTCAE Grade	Abemaciclib Dose Modifications
Grade 1 or 2	No dose modification is required.
Grade 3	Suspend dose until toxicity resolves to \leq Grade 2. Dose reduction is not required.
Grade 3, recurrent, or Grade 4	Suspend dose until toxicity resolves to \leq Grade 2. Resume at next lower dose.
Patient requires administration of a blood cell growth factor	Suspend abemaciclib dose for at least 48 hours after the last dose of blood cell growth factor and until toxicity resolves to \leq Grade 2.

CONFIDENTIAL

This material is the property of the University of Pennsylvania.

	Resume abemaciclib at next lower dose unless the dose was already reduced for the toxicity that led to the use of the growth factor.
--	--

General Guidance for Interstitial lung disease (ILD)/Pneumonitis events

Interstitial lung disease (ILD) / pneumonitis has been identified as an adverse drug reaction for abemaciclib. Adverse events reported included events such as interstitial lung disease, pneumonitis, obliterative bronchiolitis, organizing pneumonia, pulmonary fibrosis. The majority of events were Grade 1 or Grade 2 with serious cases and fatal events reported.

Monitor for clinical symptoms or radiological changes indicative of ILD/pneumonitis and please ask patients to report any new or worsening pulmonary symptoms. Symptoms may include hypoxia, cough, dyspnea, or interstitial infiltrates on radiologic exams.; these symptoms should be investigated and treated as per local clinical practice and/or guidelines (including corticosteroids as appropriate). Infectious, neoplastic, and other causes for such symptoms should be excluded by means of appropriate investigations. Investigations may include imaging such as high resolution computer tomography (HRCT), bronchoalveolar lavage (BAL), and biopsy as clinically indicated (see also Table 7: *refer to dose adjustment table for interstitial lung disease/pneumonitis*).

Table 5: Dose Modification and Management — Interstitial Lung Disease/Pneumonitis

CTCAE Grade	Abemaciclib Dose Modifications
Grade 1 or 2	No dose modification is required.

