8.4.3 Safety Analysis

All subjects entered into the study and who are given at least one dose of abemaciclib will have detailed information collected on adverse events for the overall study safety analysis. All adverse events will be categorized by CTCAE v. 5.0, tabulated as ordinal, and summarized as binomial proportions.

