9.1.2 Adverse Event

An **adverse event** (AE) is any symptom, sign, illness or experience that develops or worsens in severity during the course of the study. Intercurrent illnesses or injuries should be regarded as adverse events. Abnormal results of diagnostic procedures are considered to be adverse events if the abnormality:

- results in study withdrawal
- is associated with a serious adverse event
- is associated with clinical signs or symptoms
- leads to additional treatment or to further diagnostic tests
- is considered by the investigator to be of clinical significance

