A preexisting condition is one that is present at the start of the study. A preexisting condition should be recorded as an AE if the frequency, intensity, or the character of the condition worsens during the study period.

General Physical Examination Finding

At screening, any clinically significant abnormality should be recorded as a preexisting condition. At the end of the study, any new clinically significant findings/abnormalities that meet the definition of an AE must also be recorded and documented as an AE.

Abnormal Laboratory Values

An abnormal laboratory value that is not already associated with an AE is to be recorded as an AE only if any one of the following criteria is met:

- an action on the study drug is made as a result of the abnormality
- intervention for management of the abnormality is required
- at the discretion of the investigator should the abnormality be deemed clinically significant

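### The all-grade toxicity endpoint counts only recorded adverse events, and two conflicting rules decide when a laboratory abnormality is one, so Grade 1-2 hematologic and hepatic toxicity can be under-counted

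*Combined protocol and SAP*

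**What the plan says.** Section 2.2 sets the secondary objective "To determine toxicity rates by category using CTCAE v. 5.0". Section 8.2 describes toxicity as an ordinal measure or a dichotomized one, with no cut-point given. Under sections 7.10.6 and 8.4.3 the data are the adverse events of everyone given at least one dose of abemaciclib, "tabulated as ordinal, and summarized as binomial proportions". Section 8.4 adds 90% confidence intervals.

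Two places say when an abnormal result is an adverse event:

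- Section 9.1.4, in its paragraph on laboratory findings, has this rule: "An abnormal laboratory value that is not already associated with an AE is to be recorded as an AE only if any one of" three conditions holds. They are that "an action on the study drug is made as a result of the abnormality", that "intervention for management of the abnormality is required", or that the investigator deems the value clinically significant.
- Section 9.1.2, for diagnostic results in general, includes a result that "leads to additional treatment or to further diagnostic tests". It also lists study withdrawal, association with a serious event, association with signs or symptoms, and investigator judgment.

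Blood counts and chemistries are drawn on schedule for every subject (section 6, Schedule of Study Procedures). The plan uses CTCAE grades of these values to steer dosing and extra testing, but describes no tabulation of them.

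**The concern.** An endpoint that counts every grade needs an input that records every grade. Here the input passes through a filter that depends on what was done about a value or what the investigator thought of it. For Grade 1-2 hematologic toxicity and for non-persistent Grade 1-2 ALT, the abemaciclib tables say "No dose modification is required", so the drug-action condition is not met through abemaciclib. Unless intervention is needed or nivolumab is held, recording then rests on the judgment of an investigator in an open-label, single-arm trial.

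The second problem is consistency. Two staff members, each following a different section, can classify the same result differently. The reported low-grade rates would then partly reflect which section was followed.

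Section 1.1 assumes that the combination will be tolerable in HCC, on the strength of breast and lung cancer studies with another PD-1 inhibitor. Liver and marrow toxicity in this population is thus something the trial should measure, not take over from elsewhere.

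**Working it through.** **1. The plan's own precision figure.** Section 8.3 gives a maximum 90% interval width of 0.34 for a proportion at n = 27. The exact (Clopper-Pearson) interval is widest at 14/27: 0.347 to 0.687, width 0.340. The figure reproduces. It covers sampling error only and makes no allowance for events that were never recorded.

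**2. The two rules applied to the same finding.** Inputs are the dose tables in 3.1.1 and 3.2, footnotes 4 and 5 of the Schedule of Study Procedures, and sections 9.1.2 and 9.1.4. The subject is assumed free of symptoms and untreated for the abnormality.

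| Finding | Drug action required | AE under 9.1.4? | AE under 9.1.2? |
|---|---|---|---|
| Grade 3-4 cytopenia, possibly related to abemaciclib | Abemaciclib withheld | Yes | A hold is not listed as such; a repeat count to show recovery would qualify |
| AST/ALT more than 3 and up to 5 x ULN from a normal baseline, related to nivolumab | Nivolumab withheld | Yes, if nivolumab counts as study drug | Yes if further tests follow |
| Grade 2 cytopenia, cycle 3 or later | None | Discretion only | Yes: it triggers a day-15 count |
| Grade 1 ALT rise on day 1 of cycle 3 or later | None | Discretion only | Yes: it triggers day-15 chemistries |
| Grade 1-2 cytopenia in cycle 1 or 2, where later tests are scheduled anyway | None | Discretion only | Discretion only |

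Rows three and four show the conflict. Row five shows a gap that remains under either rule. The gap lies mainly at Grade 1-2.

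**3. What is captured above that level.** Grade 4 ALT, and Grade 3 ALT with bilirubin above 2 x ULN without cholestasis, lead to discontinuation of abemaciclib. Persistent or recurrent Grade 2 ALT, and Grade 3 ALT not resolved within 7 days, lead to suspension. All meet the first condition of 9.1.4. What can still be missed above Grade 2 is narrow: events judged unrelated, and Grade 3 ALT without raised bilirubin that settles within 7 days and causes no nivolumab hold. Each is missed only if it also needed no intervention and was not judged significant.

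**4. Size.** Let H be the true proportion of subjects whose worst grade is 3-4 (all captured), L the proportion whose worst grade is 1-2, and c the share of the latter that is recorded. Then

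recorded any-grade rate = H + cL, and shortfall = (1 - c)L.

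The documents give neither L nor c for this trial, so the shortfall cannot be derived. As an illustration only, take H = 0.19 + 0.05 = 0.24 (Grade 3 and Grade 4 neutropenia in the single-arm breast cancer study of abemaciclib 200 mg, section 1.2.1.2), and **assume** a true any-grade rate of 0.60, so L = 0.60 - 0.24 = 0.36.

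| c (assumed) | Recorded any-grade rate | Nearest count of 27 | Exact 90% interval |
|---|---|---|---|
| 1.00 | 0.60 | 16 | 0.42-0.75 |
| 0.75 | 0.51 | 14 | 0.35-0.69 |
| 0.50 | 0.42 | 11 | 0.25-0.58 |
| 0.25 | 0.33 | 9 | 0.19-0.51 |
| 0 | 0.24 | 6 | 0.10-0.39 |

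The Grade 3-4 rate stays at 0.24 throughout. At c = 0.50 the interval already excludes the assumed true rate of 0.60. With c held at 0.50, other values of L give shortfalls of 0.5 x 0.20 = 0.10 and 0.5 x 0.50 = 0.25.

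**5. Primary endpoint.** Response comes from imaging, so the recording rule does not touch it. The stated 81% power reproduces (reject at 8 or more of 27: exact alpha 0.098, power 0.812).

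**The case against.** The strongest reply is that the plan captures what matters. Related high-grade cytopenias and serious ALT events must be recorded, some Grade 2 transaminase rises are caught through the nivolumab table, and the investigator may record anything judged significant. Section 9.1.4 also makes a worsening preexisting condition an adverse event. That matters because eligibility admits AST and ALT up to 3 x ULN and bilirubin up to 2 x ULN. All of this stands, and it confines the problem mainly to isolated low-grade values in a descriptive secondary endpoint.

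A reader might go further in three ways that the documents do not support:

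- That hematologic and hepatic toxicity as a whole will be under-counted, or that the low grades will be almost absent from the table. Discretion can admit any number of these events, and no capture fraction is given.
- That the AST and ALT rates of 21% and 15% in section 1.3.1 give the size of the loss. They follow a statement about Grade 3/4 events, so they cannot be taken as Grade 1-2 rates.
- That the trial's rates cannot be compared with the single-agent figures in section 1. The documents do not say how those studies recorded laboratory events, and the abemaciclib figures there are Grade 3/4, the range largely captured here.

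It can also be said that stating plainly that the rates cover recorded adverse events only would be enough. That would be honest labelling, but it would leave the conflict between 9.1.2 and 9.1.4 in place.

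**Conclusion.** The concern holds for low grades. As written, the plan feeds an all-grade endpoint through a discretionary filter, and two sections define that filter differently. Hematologic and hepatic rates can be too low and can vary with the section followed, chiefly for isolated Grade 1-2 values. The direction is known where events are omitted; the amount is not, and the table above rests on assumed values. If toxicity is dichotomized at Grade 3 or higher, little is lost. If it is reported as any grade or as the full ordinal scale, the whole shortfall applies.

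This rests on two readings: that study drug in 9.1.4 includes nivolumab, and that the safety table is built from recorded adverse events alone, since no other source is described. The Study Summary names only abemaciclib as the investigational product. On that narrower reading, nivolumab holds would not meet the first condition and the gap would widen somewhat.

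This should be corrected. It does not threaten the primary analysis.

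**What to change.** 1. Reconcile 9.1.2 and 9.1.4 so that one rule defines a laboratory adverse event. The rule should say whether a result that leads only to an extra test counts, and whether study drug includes nivolumab.
2. In 8.4.3 and 7.10.6, add a table of the worst on-treatment CTCAE v5.0 grade for the scheduled tests (neutrophils, white cells, hemoglobin, platelets, AST, ALT, alkaline phosphatase, bilirubin, creatinine). Compute it from the measured values of every subject given abemaciclib and report it beside the adverse event table.
3. Show shift from baseline grade. Eligibility admits ALT in the range that the plan's own hepatotoxicity table calls Grade 1, so worst grade alone would count some baseline disease as toxicity. Footnote creatinine, because section 3.1.2 describes a rise without loss of glomerular function.
4. Give 90% intervals on the actual safety denominator. It may exceed 27, because subjects not evaluable for efficacy are replaced (8.4.2) but stay in the safety set.
5. State the cut-point for the dichotomized endpoint.

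The cost is protocol wording, one more programmed table, and entry of the scheduled laboratory values in the case report form if they are not already there, which section 10.2 does not say. Reported low-grade laboratory toxicity would probably be higher. No treatment rule changes.

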9.2 Adverse Event Reporting Period

The study period during which adverse events must be reported is normally defined as the period from the initiation of any study procedures to the end of the study treatment follow-up. For this study, the study treatment follow-up is defined as 30 days following the last administration of study treatment.

CONFIDENTIAL

This material is the property of the University of Pennsylvania.

9.2.1 Post-Study Adverse Event

All unresolved AEs should be followed by the investigator until the events are resolved, the subject is lost to follow-up, or the AE is otherwise explained. At the last scheduled visit, the investigator should instruct each subject to report any subsequent event(s) that the subject, or the subject's personal physician, believes might reasonably be related to participation in this study. The investigator should notify the Principal Investigator of any death or AE occurring at any time after a subject has discontinued or terminated study participation that may reasonably be related to this study. The Principal Investigator should also be notified if the investigator should become aware of the development of cancer or of a congenital anomaly in a subsequently conceived offspring of a subject that has participated in this study.

9.3 Recording of Adverse Events

At each contact with the subject, the investigator will seek information on adverse events by specific questioning and, as appropriate, by examination. Information on all adverse events will be recorded immediately in the source document, and also in the appropriate adverse event module of the case report form (CRF). All clearly related signs, symptoms, and abnormal diagnostic procedures results should be recorded in the source document, though should be grouped under one diagnosis.

All adverse events occurring during the study period will be recorded. The clinical course of each event will be followed until resolution, stabilization, or until it has been determined that the study intervention or participation is not the cause. Serious adverse events that are still ongoing at the end of the study period will be followed up to determine the final outcome. Any serious adverse event that occurs after the study period and is considered to be possibly related to the study intervention or study participation will be recorded and reported immediately.

9.4 Relationship of AE to Study

The relationship of each adverse event to the study procedures should be characterized by the Investigator as definitely related, probably related, possibly related, unlikely or unrelated to study therapy.

9.5 Reporting of Adverse Events, Adverse Device Effects and Unanticipated Problems

Investigators must conform to the adverse event reporting timelines, formats and requirements of the various entities to which they are responsible,

If the report is supplied as a narrative, the minimum necessary information to be provided at the time of the initial report includes:

Study identifier	Current status
Study Center	Whether study intervention was discontinued
Subject number	The reason why the event is classified as serious
A description of the event	Investigator assessment of the association between the event and study intervention
Date of onset	

Additionally all other events (unanticipated problems, adverse reactions, unanticipated adverse device effects and subject complaints will be recorded and reported with respect to institutional and federal policies as described in the Penn Manual and below.

9.5.1 Follow-up report

If an SAE has not resolved at the time of the initial report and new information arises that changes the investigator's assessment of the event, a follow-up report including all relevant new or reassessed information (e.g., concomitant medication, medical history) should be submitted to the IRB. The investigator is responsible for ensuring that all SAE are followed until either resolved or stable.

CONFIDENTIAL

This material is the property of the University of Pennsylvania.

9.5.2 Investigator Reporting: Notifying Drug Manufacturer (Eli Lilly)

All SAEs, AESIs, and pregnancies, regardless of relationship to study drug, must be reported to the drug manufacturer during the study through 30 days after receiving the last dose of study treatment within 1 business day, according to the procedures below. After the 30-day specified window, only SAEs considered to be treatment related and all AESIs, regardless of treatment relationship, should be reported. It is important that the investigator provide an assessment of relationship of the SAE or AESI to study treatment at the time of the initial report.

Serious adverse events should be reported to Lilly using a CIOMS Form or other form acceptable to Lilly. Investigator and Institution further agree to make available promptly to Lilly such records as may be necessary and pertinent for Lilly to further investigate an adverse event in the Study that is possibly associated with the Study Drug.

Investigator and Institution agree to provide Lilly with a copy of all information Investigator and/or Institution submit to regulators related to any adverse events for the Study Drug that occur during the Study that Investigator and/or Institution have not otherwise provided Lilly.

9.5.3 Investigator Reporting: Notifying the Penn IRB

This section describes the requirements for safety reporting by investigators who are Penn faculty, affiliated with a Penn research site, or otherwise responsible for safety reporting to the Penn IRB. The University of Pennsylvania IRB (Penn IRB) requires expedited reporting of those events related to study participation that are unforeseen and indicate that participants or others are at increased risk of harm. The Penn IRB will not acknowledge safety reports or bulk adverse event submissions that do not meet the criteria outlined below. The Penn IRB requires researchers to submit reports of the following problems within 10 working days from the time the investigator becomes aware of the event:

Any adverse event (regardless of whether the event is serious or non-serious, on-site or off-site) that occurs any time during or after the research study, which in the opinion of the principal investigator is:

Unexpected (An event is “unexpected” when its specificity and severity are not accurately reflected in the protocol-related documents, such as the IRB-approved research protocol, any applicable investigator brochure, and the current IRB-approved informed consent document and other relevant sources of information, such as product labeling and package inserts.)

AND

Related to the research procedures (An event is “related to the research procedures” if in the opinion of the principal investigator or sponsor, the event was more likely than not to be caused by the research procedures.)

9.5.4 Reporting Process

Unanticipated problems posing risks to subjects or others as noted above will be reported to the Penn IRB using the form: “Unanticipated Problems Posing Risks to Subjects or Others Including Reportable Adverse Events” or as a written report of the event (including a description of the event with information regarding its fulfillment of the above criteria, follow-up/resolution and need for revision to consent form and/or other study documentation).

Copies of each report and documentation of IRB notification and receipt will be kept in the Clinical Investigator’s study file.

9.5.5 Other Reportable Events:

For clinical drug trials, the following events are also reportable to the Penn IRB:

CONFIDENTIAL

- Any adverse experience that, even without detailed analysis, represents a serious unexpected adverse event that is rare in the absence of drug exposure (such as agranulocytosis, hepatic necrosis, Stevens-Johnson syndrome).
- Any adverse event that would cause the sponsor to modify the investigators brochure, protocol or informed consent form, or would prompt other action by the IRB to assure protection of human subjects.
- Information that indicates a change to the risks or potential benefits of the research, in terms of severity or frequency. For example:
 - An interim analysis indicates that participants have a lower rate of response to treatment than initially expected.
 - Safety monitoring indicates that a particular side effect is more severe, or more frequent than initially expected.
 - A paper is published from another study that shows that an arm of your research study is of no therapeutic value.
 - Change in FDA safety labeling or withdrawal from marketing of a drug, device, or biologic used in a research protocol.
- Breach of confidentiality
- Change to the protocol taken without prior IRB review to eliminate apparent immediate hazard to a research participant.
- Incarceration of a participant when the research was not previously approved under Subpart C and the investigator believes it is in the best interest of the subject to remain on the study.
- Complaint of a participant when the complaint indicates unexpected risks, or the complaint cannot be resolved by the research team.
- Protocol violation (meaning an accidental or unintentional deviation from the IRB approved protocol) that in the opinion of the investigator placed one or more participants at increased risk, or affects the rights or welfare of subjects.

9.6 Abramson Cancer Center Data Safety Monitoring Committee (DSMC):

Every effort should be made to report an event as a diagnosis, not as a list of symptoms. Symptoms that led to the diagnosis should be included in the event description but should not be the actual event.

Unless covered by exclusions below, Grade 3 or higher events must be reported within 10 days of knowledge.

All unexpected deaths within one business day of knowledge.

All other deaths within 30 days of knowledge. Deaths of subjects off-study for greater than 30 days from the last study treatment/intervention are not reportable unless a longer time frame is specified in the protocol.

EXCEPTIONS to AE/SAE Reporting:

Grade 3 or 4 events that are judged by a study investigator to be clearly unrelated to protocol therapy. The reason for determining that the event is unrelated must be clearly documented in the EMR.

Grade 3 or 4 events that are probably or definitely related to progression of disease as judged by a study investigator. The fact that this event is related to disease progression must be clearly document in the EMR.

Grade 3 or 4 events that are probably or definitely related to an FDA approved agent. The fact that this event is related to the FDA approved agent must be clearly documented in the EMR..

SAEs will be submitted to the DSMC through the Velos Clinical Trial Management System.

Reportable Events;

Exception

CONFIDENTIAL

A one-time, intentional action (planned prospectively) or process that departs from the IRB and CTSRMC approved study protocol, intended for one occurrence. Advance documented IRB and DSMC approval is required.

For in-house studies with a Medical Monitor or Safety Monitoring Committee (not DSMB), approval must be obtained from the Medical Monitor or Safety Monitoring Committee prior to submitting your exception request to the DSMC.

The following information must be contained in your exception request:

- When it is needed and why it is needed in that timeframe
- Has the Medical Monitor or Sponsor approved and provide the documentation of approval
- Is this an exception from eligibility, treatment, disease progression, study calendar windows, etc.
- Why the exception is needed (cite the section(s) of the protocol) along with the full clinical details of the subject. This must be determined by the sub-Investigator or PI.
- The reason why the protocol currently doesn't allow the situation for which an exception is being requested. This must be determined by the sub-Investigator or PI.
- If there are plans to amend the protocol and if not, why not.
- If additional follow-up or interventions will be required in order to protect the subject as a result of this exception.

Study Exceptions the DSMC may Reject:

Exceptions to eligibility, treatment/dosing, contraindicated treatment/therapies/interventions or safety tests for the following types of studies may be rejected by the DSMC:

- Any investigator-initiated treatment study.
- Any treatment study involving on-campus manufacturing of any component, regardless of sponsor.

To seek approval, you must provide the DSMC with strong and compelling scientific and clinical information to support your request. You should also include a statement explaining whether or not the protocol will be amended. If the protocol will not be amended your reasoning must be provided. If this situation is likely to happen again, the DSMC will require a protocol amendment.

Deviation

Any unintentional action or process that departs from IRB approval and is identified retrospectively. The deviation is reportable to the DSMC and the IRB within 10 days from the time the event becomes known to the study team only when: one or more participants were placed at increased risk of harm, or, the event has the potential to occur again, or the event has the potential to qualify as serious or continuing noncompliance.

If the PI determines that a deviation has **any potential** to impact participant safety (harm and/or risk), or the integrity of data produced from the participant, or some other overall impact on the study, the PI must report the deviation to the IRB and DSMC as described above. The IRB will make the final assessment of the impact. The DSMC will assess for additional safety and scientific integrity concerns.

The following information must be contained in your deviation report:

- When it happened? When the study team (any member) became aware
- The full description of the deviation including important dates, test results, actions taken towards the subject, etc. Also, why it happened and how it was identified.
- Was the Medical Monitor or Sponsor notified. If so, their response?
- The PIs assessment of the impact on risk, safety and/or outcome. If no impact, why. If impact, what and what will happen next.
- The corrective actions that have been implemented to date and the impact of those corrective action plans.

CONFIDENTIAL

- Future corrective action plans (if applicable) and the impact of those plans.
- If there are plans to amend the protocol (if applicable to prevent future deviations) and if not, why not.

If the PI determines that the event had no potential to impact participant safety (harm and/or risk) or the integrity of data produced from the participant, the PI must fully document his/her rationale for each category (risk, harm, and participant data).

10 Study Administration, Data Handling and Record Keeping

